1 PROTOCOL SUMMARY

Title	A Culturally-Tailored Web-Based Cognitive Behavioral Stress Management for Latino Sexual Minority Men living with HIV and Cancer	
Background	
HIV infection is associated with increased risk for several types of cancer, including but not limited to Kaposi's sarcoma, non-Hodgkin lymphoma, and anal cancer. With an increasing aging HIV-positive (HIV+) population, which includes large proportions of ethnic and sexual minority individuals, there has also been a substantial increase in the proportion of these individuals who develop and survive cancer.
 
Living with a dual-diagnosis of HIV and cancer can increase distress, as well as affect multiple aspects of health-related quality of life (HRQoL). Moreover, among dually-diagnosed individuals, those who are ethnic and sexual minorities may experience more substantial cancer survivorship disparities. For example, prior research indicated sexual minority cancer survivors experience higher distress and poorer self-rated health than their heterosexual counterparts.
 
Our prior research demonstrated the efficacy of a cognitive behavioral stress management (CBSM) intervention in improving psychosocial and health outcomes for individuals living with HIV or cancer. Thus, we propose a single-arm feasibility trial of a culturally-tailored web-based CBSM intervention for dually-diagnosed (HIV/cancer) Latino sexual minority men (SMM).
	
Objectives/Endpoints	Objectives	Endpoints
	
Primary: To examine the feasibility and acceptability of the culturally-tailored web-based SmartManage intervention among dually-diagnosed Latino SMM.
 
Secondary: To evaluate the preliminary efficacy of the culturally-tailored web-based SmartManage intervention among dually-diagnosed Latino SMM.
	
Feasibility will be examined via retention (> 85%) and attendance (> 70%) rates. We will evaluate acceptability via quantitative assessment as well as open-ended feedback.
 
Intended effects will be evaluated via examining pre-post changes in health-related quality of life, general stress, and disease/dual-diagnosis related distress using the following measures: Functional Assessment of Cancer Therapy Scale-General, Medical Outcomes Study HIV Survey, Perceived Stress Scale, and Impact of Event Scale.

Study Design	Single-arm feasibility trial	
Number of Patients/ Target Study Population	30 Latino sexual minority men living with both HIV and cancer	
Description of Sites Enrolling Participants	University of Miami Health System	
Study duration	1 year	
Statistical Analysis	The analyses will be primarily descriptive. A paired t test statistic and linear regression model will be used to compare outcome variables pre- to post-intervention. We will also estimate effect sizes for the outcome variables, which will be selected depending on which statistical test was performed and variance assumptions.	

1.0 Schema

*Data collected is
entered into REDCap

2 BACKGROUND

2.0 Study Rationale

Given the health disparities Latino SMM living with HIV and cancer experience, interventions to improve health and psychosocial outcomes are warranted. Cognitive behavioral stress management (CBSM) intervention is efficacious in reducing distress, as well as in improving overall quality of life. Prior studies have demonstrated the efficacy of CBSM in Latino men living with prostate cancer or Latino SMM living with HIV but have not included content specific to dually-diagnosed (cancer & HIV) SMM. The co-management of HIV and cancer presents a series of challenges that (a) critically impact health related quality of life and (b) have not been adequately addressed in evidence-based psychosocial interventions. The availability of culturally-tailored, evidence-based interventions that include techniques to enhance cognitive restructuring, emotion regulation, and communication, with favorable effects on psychosocial and physiological adjustment, and overall quality of life have been documented. Given that these prior intervention components have demonstrated efficacy, the current study will examine the feasibility, acceptability, and preliminary efficacy of content that has not been specifically tailored to this unique, yet growing subgroup, of Latino HIV+ SMM cancer survivors. Thus, our proposed work involves the development and testing of content that is of clinical and cultural relevance to this group: co-management of HIV and cancer, strategies for self-advocacy, partnering with the health system and health providers, intimacy and disclosure concerns regarding both conditions, assertiveness and communication skills, and self-efficacy in care coordination. This content will be grouped into 10 weekly sessions, which will be culturally-tailored to Latino SMM.

2.1 Background

With the advent of highly active antiretroviral therapy (HAART), HIV-infected individuals in the US are living substantially longer and have a life expectancy that now approximates that of the uninfected population. As such, an increasing number of individuals living with HIV, as they age, are being diagnosed with cancer.¹⁻³ Moreover, HIV infection may increase the risk for certain types of cancer, such as non-Hodgkins lymphoma and Kaposi's sarcoma.¹⁻³ Unfortunately, medical management of individuals dually-diagnosed with both HIV and cancer may be more complex, which may also increase potential for significant stress and its sequelae.¹⁻³ For example, medications used for HIV and cancer treatment may interact, increasing possibility for toxicity and detrimental side effects.^{1,2} Moreover, it may be difficult to distinguish whether a drop in CD4 count and/or constitutional symptoms among those dually-diagnosed are due to HIV infection or cancer treatment, further complicating medical management.^{1,2} All in all, dually-diagnosed individuals are at greater risk of experiencing stress due to the complex medical management of these diseases, as well as to the uncertainty associated with living with two life-threatening conditions. ***Furthermore, the stress of living with a dual diagnosis of HIV and cancer is likely compounded for ethnic and sexual minorities, who experience disparities in both HIV and cancer outcomes.***

HIV is disproportionately represented among ethnic and sexual minority men (SMM).^{4,5} The CDC estimates approximately 1 in 4 Latino SMM will be diagnosed with HIV in their lifetime.⁵ Thus, while current estimates of dually-diagnosed individuals are forthcoming, Latino SMM are likely to make up a substantial proportion of individuals living with both HIV and cancer. This is particularly alarming, given that, as described in detail below, Latino SMM experience a variety of health disparities, including those associated with the negative impact of stress, in the experience of living with each of these diseases.¹ While there has been little to no research examining health outcomes among dually-diagnosed Latino SMM, there are studies indicating Latino SMM experience disparities in both HIV and cancer-related outcomes, outlined below.

In addition to being more likely to be diagnosed with HIV than non-Latino white SMM, Latino SMM experience poorer HIV-related health outcomes once infected. For example, Latino SMM demonstrate poorer access to care than their non-Latino white counterparts.⁶ Moreover, Latino SMM may experience higher levels of HIV-associated stigma than their non-Latino counterparts.⁷ HIV stigma, in turn, has been associated with increased depression, lower levels of social support, and poorer physical health.⁸

Relative to heterosexual men, SMM living with cancer generally report heightened symptom bother as well as poorer sexual functioning, greater psychological distress, and worse health related quality of life (HRQoL).⁹⁻¹⁴ Evidence also suggests that SMM are more likely to engage in risky health behaviors, including inadequate exercise and greater rates of smoking and alcohol use, which may persist following a cancer diagnosis.⁹ SMM also report lower satisfaction with their cancer-related medical care and poor treatment satisfaction has been associated with fear of recurrence.^{15, 16} This of particular importance since fear of recurrence is one of the most common and distressing concerns reported by cancer survivors and a prior study found SMM with prostate cancer generally report greater fear of recurrence than heterosexual men.¹⁰⁻¹⁷ Additionally, Latino men experience poorer quality of life than their non-Latino white counterparts following a cancer diagnosis.¹⁸ Latino SMM may have less access to healthcare and resources for coping, *which may be exacerbated by multiple minority status.*⁶ Moreover, while prior research has shown that cultural values play a significant role in health and wellness among Latino populations living with HIV and cancer, no interventions have been tailored for Latino SMM.

3 OBJECTIVES AND ENDPOINTS

3.0 Objectives

Primary objective: To examine the feasibility and acceptability of the culturally-tailored web- based SmartManage intervention among dually-diagnosed Latino SMM.

Secondary objective: To evaluate the preliminary efficacy of the culturally-tailored web- based SmartManage intervention among dually-diagnosed Latino SMM.

3.1 Endpoints

Feasibility will be examined via retention (> 85%) and attendance (> 70%) rates. Acceptability will be evaluated via quantitative assessment as well as open-ended feedback. These assessments will measure standard dimensions of acceptability including relative advantage, compatibility, and complexity.

Intended effects will be evaluated via examining between-group pre-post changes in health- related quality of life, general stress, and disease/dual-diagnosis related distress.

4 STUDY DESIGN

4.0 Overall Design

This is a single-arm feasibility trial of a culturally-tailored web-based **SmartManage** (**Stress Management and Relaxation Training Management**) intervention. For this study, staff will utilize these primary avenues for participant recruitment: 1) the University of Miami Medicine system and its University of Miami affiliates (e.g., Sylvester Confidential

Comprehensive Cancer Center, consent to contact lists from other University of Miami investigators), 2) online advertising, via social media, and 3) collaboration with external partnering community-based organizations.

Culturally-Tailored Web-Based SmartManage Intervention: Through our prior work with cancer survivors and HIV+ SMM, we have developed, implemented, published and disseminated evidence-based manuals to managing prostate cancer survivorship or HIV infection in sexual minority men. CBSM is and evidence based, chronic disease management program, from which we derived content for the web-based SmartManage intervention for HIV+ SMM cancer survivors. The web-based SmartManage intervention includes ten 90-minute weekly therapist delivered group sessions (4-6 participants) via video conference. In the first 30 minutes, participants are taught/discuss a new stress reduction technique whereas the latter 60 minutes focus on stress- and self-management. Disease course, symptom burden, communication with intimate partner and/or family members and health care provider, impact of stress on physical and mental health and symptoms, and management of symptom burden and decrements in HRQoL are used for educational purposes and as catalysts for CBSM techniques. Participants describe stressors with an emphasis on symptoms and disruption, HRQoL and their coping responses for in-session role-plays. The SmartManage web platform has all intervention material, resources, and exercises.

We will adapt each of the SmartManage intervention components to be compatible with our participants' cultural beliefs and context by including culturally-relevant content and examples within both the didactic (website) and interactive (session) portions of the SmartManage intervention. Specifically, our intervention will be adapted to reflect the values of familism, allocentrism, health stigma, power distance, external locus of control, and male gender roles. Our adaptation will be guided by previous cultural concepts and adaptations used to inform similar CBSM studies.

4.1 Study timelines

The study will last approximately 16-20 weeks for all participants (factoring in time for recruitment, enrollment, assessment, and intervention). We anticipate it will take approximately 6 months to recruit our full sample, and study will last no more than 1 year in total.

5 STUDY POPULATION

This pilot study will include a total of 30 sexual minority Latino men who are HIV+ and survivors of cancer.

5.0 Inclusion Criteria

Participants must:

- a) Be \geq 18 years of age.
- b) Be fluent in English.
- c) Have evidence of at least one form of metastatic or non-metastatic solid tumor cancer and/or hematologic malignancy, including, but not limited to, the following types:
 - i. Oral cavity and pharynx (i.e. tongue, mouth, pharynx, etc.)
 - ii. Digestive system (i.e. esophagus, stomach, small intestine, colon, etc.)
 - iii. Respiratory system (i.e. larynx, lung, bronchus, etc.)

- iv. Urinary system (i.e. kidneys, bladder, urethra, ureters)
- v. Bone and joint
- vi. Soft tissue (including heart)
- vii. Breast (male)
- viii. Genital system (male, i.e. prostate, testis, penis, etc.)
- ix. Endocrine (i.e. thyroid, adrenal glands, pancreas, etc.)
- x. Melanoma skin cancer

- d) Be \geq 30 days post active primary treatment (i.e. surgery, radiation, and/or chemotherapy*) for their cancer. *(Note: Adjuvant therapies, such as hormone therapy for prostate cancer, etc. are not considered exclusionary).*
- e) Self-identify as a cisgender male
- f) Self-identify as Hispanic or Latino
- g) Have been diagnosed with HIV.
- h) Have reliable access to a computer/device with internet accessibility.

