5.2 Recruitment and Retention Methods

For this 1-year pilot, we plan to recruit 30 Latino HIV+ cancer survivors who are sexual minority men. By working with a variety of UM and UM-affiliated groups, including Sylvester Comprehensive Cancer Center as well as our external partners we hope to enroll HIV+ cancer survivors of diverse backgrounds, in terms of age, education, and socioeconomic status. We acknowledge that recruiting this many patients from such a unique population and within the proposed timeframe may present several challenges. However, study staff will capitalize on their working relationships with University of Miami Medicine affiliates and their connections to community partners.

Screening and Recruitment: Participants for this pilot will be recruited remotely (online or by phone). For this study, staff will utilize these primary avenues for participant recruitment: 1) the University of Miami Medicine system and its University of Miami affiliates (e.g., Sylvester Comprehensive Cancer Center, consent to contact lists from other University of Miami investigators), 2) online advertising via social media, and 3) collaboration with external partnering community-based organizations.

University of Miami Medicine and its UM affiliates (UHealth Clinics, UM Consent to Contact Database, or Other UM Investigators' Consent to Contact Lists)

A partial HIPAA waiver is requested for screening and recruitment purposes (See section 12.1.3 for HIPPA Waiver). Such a waiver is appropriate for the following reasons:

- a) This study is of no more than minimal risk to prospective patient/participants, as their participation simply involves undergoing a psychosocial intervention and providing questionnaires and does not utilize drugs, medical devices, or medical procedures of any kind.
- b) Personal identifiers obtained via the report will be used to determine patients' eligibility for enrollment only and will be destroyed as soon as possible after the determination of eligibility is made.
- c) All other personal health information (PHI) collected from patients will be obtained by self-report only. For the purpose of this pilot, study staff is *not* requesting access to enter patients' electronic medical records beyond the pre-screening.

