After receiving the lists of potentially eligible participants, study staff will contact individuals via phone using the Consent to Contact Script. If the prospective participant declines to provide verbal consent for screening, the study team member will thank them for their time and end the call. However, if the prospective participant does provide

Confidential

verbal consent, the study team member will proceed with the screening process, giving the individual the option of completing the full screener either by phone or online. *For those screened by phone*, study staff will enter patient's responses into REDCap and confirm the prospective participants' eligibility (or lack thereof) for the study. *For those who complete the online eligibility screener* (also REDCap), study staff will confirm eligibility during a follow-up phone call.

Online Advertising via Social Media

As most individuals are now using social media, such as Facebook, Instagram, and Twitter to stay connected with friends and family, it makes sense for the study team to advertise this potential research opportunity in this manner. Those who learn of the study via Facebook advertisements or other social media, will be directed to a brief online eligibility pre-screener, the responses to which will be captured in REDCap. On other similar studies utilizing Facebook ads, staff have noted that a number of people have clicked on the pilot's Facebook ads and either "liked" them or shared them on their personal pages. However, these same individuals have not then proceeded to complete the online pre-screener.

Moving forward, study staff will send a brief message to those individuals who comment explicitly on their Facebook pages that they are interested in taking part, but who have been unsuccessful in finishing the online pre-screener. If an individual simply shares or "likes" an ad for the pilot, study staff will not message them. Same procedures will be utilized for the other social media channels. Study staff will review all completed online pre- screeners and determine whether respondents appear to meet preliminary eligibility criteria. If respondents do meet these preliminary criteria, UM study staff will call these respondents to complete the screening process by phone or online.

Partnership with External Collaborator

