Potential participants may also be recruited remotely via the study team's collaboration with local community-based organizations serving LGBT individuals. These community-based organizations provide social services specifically for sexual minority men living with HIV and have longstanding relationships with university investigators. These organizations may advertise the study to their patrons. If someone who is not currently a UM patient, or who is a UM patient that has not been identified by the staff as a potential participant, calls our external community partners to inquire about general research opportunities, they will be redirected to our staff who will provide them with information about the study and ask for their verbal consent to complete the screening process by phone or online. In addition, we will recruit participants through referrals from enrolled participants. Enrolled participants will receive \$20 for every referral of a potentially eligible person (i.e., adult male with HIV and cancer).

Other avenues for participant recruitment

We will advertise this trial in online recruitment platforms (e.g., ResearchMatch) that help connect researchers with individuals interested in learning about research study opportunities. First, we will enter our inclusion criteria to generate a list of potentially eligible participants. Then, we will send a contact message to these individuals (See *ResearchMatch message*). Once the individual has authorized to release their contact information to our study team, we will call these respondents to complete the screening process by phone or online.

Financial Compensation:

Participants will receive a \$75 electronic payment (e.g., Zelle, digital gift card) at each of two assessments (baseline, post-intervention), and additional \$25 for participating in a

final interview (A total of \$175 for study participation).

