6 STUDY PROCEDURES

Study staff will follow guidelines from the CTSI on e-consenting using REDCap. After consent has been obtained, study staff will instruct the participant to complete the intake questionnaire.

Intake questionnaire:

- a) **Demographics and Disease Information:** Participants will complete: a demographic survey which will include factors such as age, race, education, employment status, income, nativity, years in the US, and relationship status. Participants will also complete a disease information form, which will collect medical history relevant to their cancer and HIV diagnoses. Finally, participants will complete ACTG HIV medication Adherence measure,¹⁹ and the Barriers to HIV Care survey.²⁰
- b) **Psychosocial Factors:** Participants will complete the Coping Self-Efficacy scale,²¹ Interpersonal Support Evaluation List (ISEL),²² the Bidimensional Acculturation Scale for Hispanics,²³ and the Computer Proficiency Questionnaire (CPQ).²⁴
- c) **Intervention Outcomes:** Participants will complete: the Perceived Stress Scale (General Stress),²⁵ the Impact of Event Scale (Disease/Dual-diagnosis-related Distress),²⁶ and The Functional Assessment of Cancer Therapy scale-General (FACT-G; HRQoL),²⁷ and Medical Outcomes Study HIV Survey (MOS-HIV; HRQoL).¹⁹
- d) **COVID-19 Questions:** Participants will complete the COVID-19 Impact of the Pandemic and HRQOL in Cancer Patients and Survivors measure.
- e) **Computer Proficiency:** Measured with the Computer Proficiency Questionnaire.

Once participants complete the intake questionnaire, they will be prompted to register on the culturally-tailored SmartManage intervention website. Study staff members who have previous experience and expertise in delivering CBSM interventions to Latino populations will conduct the study intervention interactive sessions. Following the intervention, participants will be prompted to complete their exit questionnaire in REDCap.

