11 STATISTICAL METHODS

11.0 Statistical Hypothesis

Primary research question: To examine the feasibility and acceptability of the culturally-tailored web-based SmartManage intervention among dually-diagnosed Latino SMM.

Primary Hypothesis: The culturally-tailored web-based SmartManage intervention will be feasible and acceptable to dually-diagnosed Latino SMM.

Secondary research question: To evaluate the preliminary efficacy of the culturally-tailored, web-based SmartManage intervention among dually-diagnosed Latino SMM.

Secondary Hypothesis: The culturally-tailored web-based SmartManage will show preliminary reductions in stress and disease-related distress and improvements quality of life among dually-diagnosed Latino SMM.

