11.2.2 Analysis of the Primary Endpoint(s)

Feasibility will be analyzed using attendance and retention rates. For the proposed study to be considered feasible, we will need to uphold all the following criteria: 70% of participants attend all intervention sessions and 85% of participants are retained throughout the study (from pre-intervention to post-intervention assessment). These proportions are based on previously successful CBSM trials in other populations.

We will also perform descriptive analyses to better understand the feasibility of our future R01 trial, including:

- 1) Personnel time: This will include personnel time that is devoted to assessing eligibility, managing contacts, and recruiting, conducting the intervention, and administrative time.
- 2) Space: We will collect information on any space used that is needed to conduct the intervention, including administrative space.
- 3) Supplies: We will collect information on all supplies that are needed and any costs associated with maintaining the SmartManage website.

Acceptability will be analyzed using the proportion of the number of participants who agree to participate in the intervention. We will evaluate the acceptability of the intervention two ways:

1) via the proportion of eligible SMM who agree to participate vs. decline and 2) via the exit survey that will measure acceptability of the intervention.

We will explore whether feasibility and acceptability differ by sociodemographic, medical, and psychosocial factors via Fisher's exact tests. These analyses will be primarily descriptive and will provide the basis for future randomized trials to formally evaluate the efficacy of the culturally-tailored web-based SmartManage intervention among dually-diagnosed Latino SMM.

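### The trial is described as one in Latino sexual minority men, but no eligibility criterion requires sexual minority status

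*Combined protocol and SAP*

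**What the plan says.** The prose on the population is consistent. The summary in section 1 gives the target as 30 Latino sexual minority men with HIV and cancer. Section 5 opens with "This pilot study will include a total of 30 sexual minority Latino men who are HIV+ and survivors of cancer", and section 5.2 says "we plan to recruit 30 Latino HIV+ cancer survivors who are sexual minority men".

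The operative list is in section 5.0, as criteria a to h. On gender it requires that the participant "Self-identify as a cisgender male" (criterion e). Latino ethnicity is criterion f and HIV diagnosis is criterion g. No letter concerns sexual orientation or behavior, and exclusions a to f in section 5.1 do not mention either.

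The analysis sections assume the narrower population. The hypothesis in section 11.0 is that the intervention "will be feasible and acceptable to dually-diagnosed Latino SMM". Section 11.2.2 measures acceptability in part "via the proportion of eligible SMM who agree to participate vs. decline".

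**The concern.** Apart from sexual minority status, every element that defines the target population has its own lettered criterion. Read as a checklist, the criteria admit heterosexual Latino men with HIV and cancer, whom the title, objectives and hypotheses leave out.

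Two things are at stake. First, the attendance and retention rates are meant to describe Latino SMM, but no checkable criterion ensures that the men counted belong to that group. Second, the acceptability proportion needs a count of eligible SMM, including those who decline. Men who decline never reach the intake questionnaire, so their status has to be established at screening. The protocol does not say how it is established, or whether SMM is defined by identity, behavior or both.

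**Working it through.** **Step 1: population against criteria.** Each defining element of the population in section 5 is set against sections 5.0 and 5.1.

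| Element of the stated population | Criterion |
|---|---|
| Cancer survivor | Inclusion c and d; exclusions a and b |
| Man | Inclusion e |
| Latino | Inclusion f |
| HIV | Inclusion g |
| Sexual minority | None |

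Inclusions a, b and h cover age, English fluency and internet access. Exclusions c to f cover severe mental illness, alcohol, substances and life expectancy. The count that mention sexual minority status is 0 of 8 inclusions and 0 of 6 exclusions. The lettering is unbroken in both lists, so there is no sign that an item was lost when the text was extracted.

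**Step 2: whether other text supplies the rule.**

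- *Online platforms (5.2).* The search works from the criteria themselves: "First, we will enter our inclusion criteria to generate a list of potentially eligible participants". It inherits the omission, although the men it finds are screened afterwards.
- *Chart review, contact database and referrals (5.2).* None of these descriptions names orientation. They are incomplete on other points too: the referral description omits ethnicity, and the database filter omits HIV. Their silence is therefore weak evidence about final eligibility.
- *Community organizations (5.2).* These serve sexual minority men with HIV, but they are one route among several.
- *Screener (5.2).* Prospective participants are screened by "giving the individual the option of completing the full screener either by phone or online". The form is not reproduced and may ask about orientation.
- *Intake form (6).* It includes "a demographic survey which will include factors such as age, race, education, employment status" and further items, none of them orientation. The list is illustrative, so this does not show that orientation goes unrecorded.

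No text in the documents supplies the missing criterion. Nor do they show that orientation is never asked.

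**Step 3: scale.** The plan gives no figure that depends on this point, so the following is illustration and not prediction. The interval is exact (Clopper-Pearson) at 95%: for x of n, the lower limit is the 0.025 quantile of Beta(x, n − x + 1) and the upper limit is the 0.975 quantile of Beta(x + 1, n − x).

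- Table 1 in section 11.1 is reproduced first: 21/30 = 70.0%, interval 50.6% to 85.3%. This matches.
- Assume one of the 30 is not SMM. His share is 1/30 = 3.3%.
- If he attended all sessions, the SMM rate is 20/29 = 69.0%, interval 49.2% to 84.7%.
- If he did not, it is 21/29 = 72.4%, interval 52.8% to 87.3%.

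The intervals barely move. The point estimate can still cross the feasibility line. With the 70% of section 11.2.2 read as at least 70%, 21/30 meets it and 20/29 does not. With the wording of section 3.1 (more than 70%), 21/30 fails and 21/29 passes. This happens only because the example sits on the threshold.

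**The case against.** The strongest reply is that the restriction is stated, only not lettered. The opening sentence of section 5 governs 5.0 and 5.1, and a heterosexual man fails that sentence even if he meets a to h. Eligible SMM can then be read as SMM who meet the listed criteria, and section 11.2.2 presupposes that status is known by then. The screener probably asks, men found on a recruitment platform are screened before enrollment, and no harm to any result has been shown.

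Much of this stands. The intent is clear, the omission looks like a drafting slip, and the numerical effect is unknown. If the screener records orientation, the denominator can be counted in practice.

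It does not remove the mismatch. Gender, ethnicity and HIV also appear in the prose, and each was still given a criterion. Section 5.0 is introduced as what participants must satisfy, and the platform search is built from it. If the screener does apply an orientation rule, staff are enforcing an eligibility condition that the criteria do not contain and whose definition the protocol does not give.

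**Conclusion.** The concern holds. The eligibility criteria as written admit men outside the population named in section 5 and in the primary hypothesis, and the SMM denominator for one of the two acceptability measures has no written definition. The gap itself is certain from the text.

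Its effect on results cannot be sized, because the documents give no count of non-SMM participants and do not reproduce the screener. The one-man illustration assumes 21 of 30 attend all sessions. It shows a shift of about 1 percentage point down (70.0% to 69.0%) or 2.4 points up (70.0% to 72.4%), with almost no change in precision. The weight of the point lies in whom a single-arm feasibility estimate describes, which matters because section 11.2.2 intends it to inform a future trial. It should be fixed.

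**What to change.** Reconcile sections 5 and 5.0 by adding a self-reported sexual minority criterion, with the sponsor stating whether it rests on identity, behavior or both. Confirm that the full screener and the baseline form record it, and add the item where it is absent. In section 11.2.2, define eligible SMM from that screening item so that men who decline are counted on the same basis as those who agree.

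Section 12.0.3 refers to former and current participants, so enrollment had begun and a new criterion cannot act on those men. First establish what the screener recorded for them. If status was not recorded, check records or recontact them. Then report how many are confirmed SMM and show attendance and retention for that group beside the full sample. The referral description in section 5.2 can stay as it is, so that participants are not asked to judge another man's orientation.

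The cost is a minor IRB amendment: one criterion, a check of two forms and one definition. If status was not recorded, add the recontact work and one descriptive table. The downside is slightly more screen failures in a population that section 5.2 already expects to be hard to recruit.
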